7.7 PROPHYLACTIC MEDICATIONS, TREATMENTS, AND PROCEDURES

- Subjects may be pre-medicated for nausea and vomiting at investigator discretion.
- Patients may receive ongoing supportive and palliative care (e.g. pain control) as clinically indicated throughout the study.
- Prophylactic use of anti-infectives is highly recommended during the period of profound neutropenia until ANC returns to 500/ μ L or greater. The choice of anti-infectives will be per Moffitt institutional standard of care.
- Growth factor support will be administered according to Moffitt protocol.
- The use of transfusion support (RBCs and platelets) will be according to standard of care.

7.8 RESCUE MEDICATIONS, TREATMENTS, AND PROCEDURES

- Growth factor support with granulocyte stimulating factor will be administered according to Moffitt protocol for the treatment of cytopenias
- The use of transfusion support (RBCs and platelets) will be according to standard of care as rescue therapy for anemia or thrombocytopenia.
- Corticosteroids and antihistamines may be administered per Moffitt protocol for the treatment of hypersensitivity reactions should they emerge.

8 ASSESSMENT OF SAFETY

8.1 SPECIFICATION OF SAFETY PARAMETERS

8.1.1 DEFINITION OF ADVERSE EVENTS (AE)

An adverse event means any untoward medical occurrence associated with the use of an intervention in humans, whether or not considered intervention-related (21 CFR 312.32 (a)).

The investigator or qualified designee will assess each subject to evaluate for potential new or worsening AEs as specified in the Schedule of Events and more frequently if clinically indicated. Adverse experiences will be graded and recorded throughout the study and during the follow-up

period. The descriptions and grading scales found in the revised NCI Common Terminology Criteria for Adverse Events (CTCAE) version 5.0 will be utilized for adverse event reporting. (<http://ctep.cancer.gov/reporting/ctc.html>)

Toxicities will be characterized in terms regarding seriousness, causality, toxicity grading, and action taken with regard to trial treatment.

8.1.2 DEFINITION OF SERIOUS ADVERSE EVENTS (SAE)

Adverse events and suspected adverse reactions are considered "serious" if, in the view of either the investigator or sponsor, they result in any of the following outcomes: death, a life-threatening adverse event, inpatient hospitalization or prolongation of existing hospitalization, a persistent or significant incapacity or substantial disruption of the ability to conduct normal life functions, or a congenital anomaly/birth defect. Important medical events that may not result in death, be life-threatening, or require hospitalization may be considered serious when, based upon appropriate medical judgment, they may jeopardize the patient or subject and may require medical or surgical intervention to prevent one of the outcomes listed in this definition.

8.1.3 DEFINITION OF UNANTICIPATED PROBLEMS

Unanticipated problems (UPs) involving risks to participants or others to include, in general, any incident, experience, or outcome that meets **all** of the following criteria:

- Unexpected in terms of nature, severity, or frequency given (a) the research procedures that are described in the protocol-related documents, such as the IRB-approved research protocol and informed consent document; and (b) the characteristics of the participant population being studied;
- Related or possibly related to participation in the research ("possibly related" means there is a reasonable possibility that the incident, experience, or outcome may have been caused by the procedures involved in the research); and
- Suggests that the research places participants or others at a greater risk of harm (including physical, psychological, economic, or social harm) than was previously known or recognized.

8.2 CLASSIFICATION OF AN ADVERSE EVENT

8.2.1 SEVERITY OF EVENT

All AEs will be graded using the CTCAE 5.0 criteria.

For AEs not included in the protocol-defined grading system, the following guidelines will be used to describe severity.

- **Mild** – Events require minimal or no treatment and do not interfere with the participant's daily activities.
- **Moderate** – Events result in a low level of inconvenience or concern with the therapeutic measures. Moderate events may cause some interference with functioning.
- **Severe** – Events interrupt a participant's usual daily activity and may require systemic drug therapy or other treatment. Severe events are usually potentially life-threatening or

incapacitating.

8.2.2 RELATIONSHIP TO STUDY AGENT

For all collected AEs, the investigator will evaluate the participant and will determine the AE's causality based on temporal relationship and his/her clinical judgment. The degree of certainty about causality will be graded using the categories below.

- **Definitely Related** – There is clear evidence to suggest a causal relationship, and other possible contributing factors can be ruled out. The clinical event, including an abnormal laboratory test result, occurs in a plausible time relationship to drug administration and cannot be explained by concurrent disease or other drugs or chemicals. The response to withdrawal of the drug (dechallenge) should be clinically plausible. The event must be pharmacologically or phenomenologically definitive, with use of a satisfactory rechallenge procedure if necessary.
- **Probably Related** – There is evidence to suggest a causal relationship, and the influence of other factors is unlikely. The clinical event, including an abnormal laboratory test result, occurs within a reasonable time after administration of the drug, is unlikely to be attributed to concurrent disease or other drugs or chemicals, and follows a clinically reasonable response on withdrawal (dechallenge). Rechallenge information is not required to fulfill this definition.
- **Possibly Related** – There is some evidence to suggest a causal relationship (e.g., the event occurred within a reasonable time after administration of the trial medication). However, other factors may have contributed to the event (e.g., the participant's clinical condition, other concomitant events). Although an AE may rate only as "possibly related" soon after discovery, it can be flagged as requiring more information and later be upgraded to "probably related" or "definitely related," as appropriate.
- **Unlikely to be related** – A clinical event, including an abnormal laboratory test result, whose temporal relationship to drug administration makes a causal relationship improbable (e.g., the event did not occur within a reasonable time after administration of the trial medication) and in which other drugs or chemicals or underlying disease provides plausible explanations (e.g., the participant's clinical condition, other concomitant treatments).
- **Unrelated** – The AE is completely independent of study drug administration, and/or evidence exists that the event is definitely related to another etiology. There must be an alternative, definitive etiology documented by the clinician.

8.2.3 EXPECTEDNESS

The PI will be responsible for determining whether an AE is expected or unexpected. An AE will be considered unexpected if the nature, severity, or frequency of the event is not consistent with the risk information previously described for the study agent.

8.3 TIME PERIOD AND FREQUENCY FOR EVENT ASSESSMENT AND FOLLOW-UP

The occurrence of an AE or SAE may come to the attention of study personnel during study visits and interviews with study participants presenting for medical care, or upon review by a study monitor. All AEs, including local and systemic reactions not meeting the criteria for SAEs, will be captured on the appropriate CRF. Information to be collected includes event description, time of onset, clinician's assessment of severity, relationship to study product (assessed only by those with the training and authority to make a diagnosis), and time of resolution/stabilization of event. All AEs occurring during the study must be documented appropriately, regardless of relationship. All AEs will be followed to adequate resolution.

Any medical condition that is present at the time that the participant is screened will be considered as baseline and not reported as an AE. However, if the study participant's condition deteriorates at anytime during the study, it will be recorded as an AE. UPs will be recorded in the data collection system throughout the study.

Changes in the severity of AEs will be documented to allow an assessment of the duration of the event at each level of severity to be performed. AEs characterized as "intermittent" require documentation of onset and duration of each episode in the medical record.

Adverse events for the purpose of this study will be will be reported from the time period beginning when the consent form is signed until 30 days after study drug discontinuation. Events will be followed for outcome information until resolution or stabilization is achieved. Any AE present at the time of final study closure will be considered ongoing.

8.4 REPORTING PROCEDURES

8.4.1 ADVERSE EVENT REPORTING

Adverse event documentation will be performed by entry into the Moffitt OnCore electronic database. Reporting of adverse events to the FDA for IND renewal will occur annually by a report obtained from the AEs collected in OnCore. Reporting to Jazz Pharmaceuticals will be as noted in the section on AEs of special interest.

All AEs will be documented on a paper log with columns for the replication of the fields in the OnCore AE data form. The treating physician/investigator will review the log for accuracy and assign CTCAE grade and the attribution of a study agent to the AE.

Adverse events for the purpose of this study will be reported from the time period beginning when the consent form is signed until 30 days after study drug discontinuation.

8.4.2 SERIOUS ADVERSE EVENT REPORTING

All SAEs will be followed until satisfactory resolution or until the site investigator deems the event to be chronic or the adherence to be stable. Other supporting documentation of the event may be requested by Jazz Pharmaceuticals, Inc. and should be provided as soon as possible. Moffitt as the study sponsor will be responsible for notifying FDA of any unexpected fatal or life-threatening suspected adverse reaction as soon as possible but in no case later than 7 calendar days after the sponsor's initial receipt of the information.

8.4.3 UNANTICIPATED PROBLEM REPORTING

Incidents or events that meet the OHRP criteria for UPs require the creation and completion of an UP report form. It is the site investigator's responsibility to report UPs to their IRB and to Jazz Pharmaceuticals, Inc. The UP report will include the following information:

- Protocol identifying information: protocol title and number, PI's name, and the IRB project number;
- A detailed description of the event, incident, experience, or outcome;

- An explanation of the basis for determining that the event, incident, experience, or outcome represents an UP;
- A description of any changes to the protocol or other corrective actions that have been taken or are proposed in response to the UP.

To satisfy the requirement for prompt reporting, UPs will be reported using the following timeline:

- UPs that are SAEs will be reported to the IRB and to the study sponsor within 24 hours of the investigator becoming aware of the event.
- Any other UP will be reported to the IRB and to the study sponsor within 2 business days of the investigator becoming aware of the problem.
- All UPs should be reported to appropriate institutional officials (as required by an institution's written reporting procedures) and the supporting agency head (or designee), within 7 days of the IRB's receipt of the report of the problem from the investigator.

8.4.4 EVENTS OF SPECIAL INTEREST

1. **Cardiotoxicity:** Current studies estimate the risk of cardiotoxicity to be low, perhaps related to the liposomal formulation. However, given that patients will have likely had prior anthracycline exposure (up to a maximum of 368 mg/m² daunorubicin or equivalent), we will obtain baseline echocardiogram or MUGA to ensure adequate ejection fraction. Followup echocardiogram or MUGA will be performed in all patients with symptomatic heart failure, defined as follows: worsening 1) dyspnea on exertion, 2) orthopnea, and/or 3) paroxysmal nocturnal dyspnea - with following concomitant findings of fluid overload on exam not well explained by prior therapy (such as hydration related to an episode of sepsis), including: 1) development of a third heart sound, 2) jugular venous distention with positive hepatojugular reflex, 3) pulmonary rales, and/or 4) lower extremity edema (ref 31). Follow-up echocardiogram or MUGA prior to each cycle of consolidation will be performed for all patients exceeding 550 mg/m² daunorubicin (or equivalent) . Patients with an ejection fraction of <50% or a decrease of >10% from baseline will discontinue consolidation therapy. The development of symptomatic heart failure and/or decrease in ejection fraction to <50%, or >10% from baseline will be reported to Jazz Pharmaceuticals.
2. **Bone marrow aplasia:** Liposomal delivery of chemotherapy may facilitate increased deposition within hematopoietic stem cells, culminating in delay or failure to recover hematopoietic cell reconstitution following therapy. In particular, a hypocellular marrow without adequate count recovery >42 days from start of induction or consolidation cycles will be reported to the sponsor.

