2.2 RATIONALE

Remission rates vary considerably depending on population studies (children vs adults), relapsed vs refractory status, and timing of salvage (first relapse vs beyond first relapse) making it difficult to extrapolate baseline rate. If focusing specifically on 2 trials that used an induction composed of cytarabine (3gm/m² x5d) and idarubicin (40mg/m² on d3), complete remission rates are approximately 40% (38-44%, total n=54). (ref 4-5). Alternatively, a more recent phase 3 trial of inotuzumab vs standard of care in patients in first or second relapse shows a composite CR rate in the standard of care arm (Cytarabine+Mitoxantrone, high dose Cytarabine, and Fludarabine, Cytarabine, and GCSF, total n=109) of 29%. (ref 13). Given these data, it is determined that a baseline CR rate of 35% is likely to estimate activity with a standard salvage regimen.

Data using liposomal anthracyclines among those with relapsed ALL, including FLAD (Fludarabine, Cytarabine, Liposomal Daunorubicin) and Cytarabine+Liposomal Daunorubicin, have shown an improvement in CR rates, at 65% and 80%, respectively. (ref 18,28) Together these data suggest a CR rate of 65% should be attainable using CPX-351.

However, at this stage, a phase 2 pilot trial is proposed to explore response rates among 10 patients with ALL. Should sufficient activity be observed, consideration may be made in consultation with Jazz

Pharmaceuticals, to increase the budget to increase accrual to formally test our hypothesis, possibly in a multicenter setting.

Safety will be monitored as per standard routine, accounting for adverse events using CTCAE v. 5.0. Myelotoxicity is anticipated, in addition to associated infections. Frequency of these events will be monitored for comparison with historical rates, referencing against historical regimens noted above. Adverse events of special interest include bone marrow aplasia (hypocellular marrow without adequate count recovery >42 days from start of therapy), and *symptomatic* heart failure (accompanied by a decrease in the ejection fraction >10% from baseline greater than 42 days from start of therapy).

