7.1.13 Bone Marrow Biopsy

A bone marrow biopsy will be performed at screening and at day 28. If determined the subject has extramedullary disease (as permitted in inclusion criterion #4), biopsy of the involved area will be the method by which correlative samples will be obtained, provided this can be safely obtained. If extramedullary disease is confirmed and the bone marrow biopsy is shown to be negative prior to trial participation, no bone marrow biopsy will be required at day 28. If subject discontinues treatment early or progression of disease is suspected, a bone marrow biopsy will be done at the discretion of the investigator. During follow-up, bone marrow biopsies will be performed per investigator discretion.

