- f. Serum chemistry testing will include the following: albumin, BUN, creatinine, alkaline phosphatase, ALT, AST, CO₂, calcium, chloride, glucose, potassium, sodium, total bilirubin, total protein.
- g. The EOT visit will occur 30 days (+10 days) after the last dose of study drug or before the start of subsequent antineoplastic therapy if that occurs sooner.
- h. Correlative studies will be performed as below:
 1. BH3 protein- bone marrow/core biopsy
 2. Ex vivo drug sensitivity assay- bone marrow/core biopsy
 3. T-cell profile- bone marrow/core biopsy/peripheral blood
 4. PDL1 immunohistochemistry- bone marrow/core biopsy
- i. After induction day 28 and through consolidation therapy, laboratory testing will be continued as necessary per standard of care.
- j. Only obtained at screening if symptomatic. Per standard of care, CSF (if no contraindications) will be obtained 7-10 days after initiation of CPX dosing and IT methotrexate will be administered. See Section 7.1.15.
- k. Bone marrow biopsy will be at screening and day 28 of induction therapy. During consolidation therapy, a bone marrow biopsy will be performed on day 28 (+7 days) after the start of each consolidation per standard of care.
- l. Echocardiogram will be repeated for any patient with >550mg/m² daunorubicin (or daunorubicin anthracycline equivalent) exposure. Therapy will only be permitted if the ejection fraction remains >50% and without >10% decrease in ejection fraction from baseline.
- m. CT or PET/CT scan will be utilized at screening and Day 28 as response assessment for subjects with extramedullary disease or for staging purposes as determined by the investigator.

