10.4.3 ANALYSIS OF THE SECONDARY ENDPOINT(S)

- Minimal Residual Disease (MRD) will be studied as a dichotomous endpoint using a cutoff of 1×10^{-4} cells/transcripts as the lower limit for residual leukemia, and presented as the percentage of patients reaching this landmark as their best response. MRD assessment will be obtained with each bone marrow biopsy assessment, as described below.
- Progression Free Survival and Overall Survival will be reported as per Cheson and Lugano Criteria, and analyzed using a standard Kaplan-Meier approach. Patients will undergo bone marrow biopsy evaluation after each cycle of therapy per standard of care to facilitated assessment. Patients achieving CR/CRi at the end of consolidation with marrow involvement will have follow-up bone marrow biopsy evaluation every 3 months in the first year following their last cycle of therapy, and every 6 months in the subsequent 2 years following their last cycle. Patients who remain in remission greater than 3 years from their last cycle of therapy will have bone marrow biopsy evaluation performed as needed. Patients without marrow involvement will have follow-up imaging (CT or PET/CT) every 3 months in the first year following their last cycle of therapy, and every 6 months in the subsequent 2 years following their last cycle. Patients progressing to allogeneic transplant following therapy will be censored at the time of conditioning.
- Safety will be continually assessed during the course of induction and consolidation cycles. Safety assessment will continue at a minimum of every 3 months for those who do not progress to allogeneic transplant or alternative therapy.

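### The aplasia event of special interest turns on day 42 of a cycle, but no on-treatment marrow is scheduled after day 35 and adverse event capture can close first, so its count rests largely on discretionary biopsies.

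*Combined protocol and SAP*

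**What the plan says.** Section 8.4.4 gives the event as "a hypocellular marrow without adequate count recovery >42 days from start of induction or consolidation cycles will be reported to the sponsor". Section 2.2 also lists it as an event of special interest, but with a different clock: "bone marrow aplasia (hypocellular marrow without adequate count recovery >42 days from start of therapy". Section 10.4.4 will tabulate events of special interest.

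The marrow schedule is in footnote k of the table in section 7.3.7. For induction: "Bone marrow biopsy will be at screening and day 28 of induction therapy". For consolidation: "a bone marrow biopsy will be performed on day 28 (+7 days) after the start of each consolidation per standard of care".

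Outside those days, section 7.1.13 leaves the marrow to judgement: "If subject discontinues treatment early or progression of disease is suspected, a bone marrow biopsy will be done at the discretion of the investigator", and "During follow-up, bone marrow biopsies will be performed per investigator discretion". Section 10.4.3 differs on follow-up. Patients with marrow involvement who are in CR/CRi when consolidation ends "will have follow-up bone marrow biopsy evaluation every 3 months in the first year following their last cycle of therapy".

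For extramedullary disease with a negative marrow before the trial, section 7.1.13 says "no bone marrow biopsy will be required at day 28". Sections 7.3.2.9, 7.3.2.13 and 7.3.2.16 likewise ask for on-treatment marrows only where the screening marrow was positive.

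Footnote i of the table puts laboratory tests after induction day 28 on routine care, with no fixed days. Footnote c and sections 8.3 and 8.4.1 close adverse event capture 30 days after CPX-351 stops.

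**The concern.** The event combines marrow cellularity, blood counts and a time limit. The plan fixes none of the three at the time when the event becomes definable. The patient who matters most is the one whose counts do not recover after induction and who gets no consolidation. That patient has no scheduled marrow after day 28, no fixed count days, and an adverse event window that normally shuts before day 43.

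Section 8.4.4 explains why this toxicity deserves attention with a liposomal product, and sections 10.2 and 10.5 say the pilot data are meant to support an expansion or a later study. If the safety table shows no aplasia, its reader needs to know whether patients were assessed and found negative, or were not assessed.

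**Working it through.** The plan gives no figure to reproduce here. The check is day arithmetic on its own schedule, with doses on time.

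**First qualifying day.** More than 42 days from cycle start means day 43 at the earliest.

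**Scheduled on-treatment marrows (7.3.7, footnote k)**
- Induction: day 28. Gap to day 43: 43 − 28 = 15 days.
- Consolidation: day 28 to 28 + 7 = 35. Smallest gap: 43 − 35 = 8 days.
- Appendix A allows an optional repeat 5 to 7 days after an ambiguous marrow. The latest repeat is 28 + 7 = day 35 in induction and 35 + 7 = day 42 in consolidation. Neither is past day 42.

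**Adverse event window (30 days past the last dose, if no further dose is given)**
- Induction, last dose day 5: 5 + 30 = day 35, which is 8 days before day 43.
- Consolidation, last dose day 3: 3 + 30 = day 33, which is 10 days before day 43.
- The end of treatment visit (30 to 40 days after the last dose) falls on days 35 to 45 or 33 to 43. Section 7.3.2.17 lists an adverse event assessment there but no marrow. Only the end of that visit window reaches day 43.

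**Scheduled marrows that do pass 42 days**
- The 3-monthly marrows of section 10.4.3. Taking 3 months as 91 days, the first falls about day 91 from the start of the last cycle, or 28 + 91 = day 119 if counted from the end of a 28-day cycle. They apply only to the CR/CRi group at the end of consolidation, and they conflict with the discretionary follow-up marrows in section 7.1.13.
- On section 2.2's origin, the first consolidation marrow also qualifies. With consolidation starting 28 to 75 days after induction (7.3.2.11), it falls 28 + 28 = 56 to 75 + 35 = 110 days from induction day 1. With the earliest start of 35 days in footnote d, the lower end is 35 + 28 = 63. It exists only for patients who go on to consolidation.

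**Count limit.** Section 8.4.4 gives no value for adequate recovery. Section 7.3.2.11 names ANC above 500/µL and platelets above 50,000/µL in its conditions for starting consolidation. Appendix A uses 1,000/µL and 100,000/µL for CR. A patient between the two sets is a case under one and not under the other.

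**Size.** With 10 patients, one unrecognised case changes the observed rate by 1/10 = 10 percentage points.

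**The case against.** The strongest reply is grammatical. The 42-day limit can be read as applying to count recovery alone, since recovery is what takes time. A hypocellular marrow on day 28 to 35, followed by counts still low after day 42, would then meet the definition with no extra biopsy. That reading is reasonable, and the fix below adopts it. But the text does not state it, and the later counts it needs have no fixed days.

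Other points also carry weight. Induction patients stay in hospital until their marrow recovers, with testing until discharge, so late counts will often exist. Discretionary biopsies are allowed, and a clinician facing prolonged aplasia may well do one. Section 8.3 follows recorded events to resolution, section 10.4.3 continues safety assessment at least 3-monthly for some patients, and the reporting duty in section 8.4.4 carries no end date. These make detection possible, but do not make assessment uniform or visible in the table. The continuing safety assessment also needs reconciling with the 30-day window.

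A reader might infer that the schedule cannot establish the event at all, or that the chance of detecting it is zero. The documents do not support that: the alternative reading, the 3-monthly marrows and the section 2.2 origin each allow a case to be established from planned marrows.

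Finally, this is a descriptive pilot with exploratory endpoints, and section 8.5 ties no halting rule to an aplasia count. That limits the consequence; it does not settle what the tabulated number means.

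**Conclusion.** The concern holds as an ascertainment gap. No on-treatment marrow is scheduled beyond day 35 of a cycle. In a patient who does not recover after induction and gets no consolidation, a marrow after day 42 is discretionary. Capture normally closes 8 to 10 days before the event can first qualify. The timing of the marrow, the count limit and the time origin are left open or stated inconsistently. Following the plan can therefore under-count the event, and a zero could reflect non-assessment.

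The day figures assume doses on time and no further cycle. The documents do not allow an estimate of how many cases would be missed, because the frequency of discretionary biopsies and late counts is unknown. The primary endpoint is unaffected.

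**What to change.** Make the event derivable from data the trial already expects to hold, and use one wording in sections 2.2 and 8.4.4:

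- Keep hypocellularity in the definition. State that it may come from the most recent marrow of that cycle, including the scheduled day 28 to 35 marrow.
- Combine it with counts still below one stated ANC and platelet limit after day 42, counted from the start of that cycle.
- State that this event is captured beyond the 30-day adverse event window.
- Classify patients with low counts after day 42 but no marrow in that cycle, such as those with extramedullary disease only, separately as prolonged cytopenia, marrow not assessed.
- Report cases over patients assessable after day 42. I would count documented earlier recovery to the stated limit as assessed and negative, so that recovered patients who move on are not lost from the denominator.
- Reconcile sections 2.2, 7.1.13, 7.3.7 (footnotes c, i and k), 8.3, 8.4.1, 8.4.4 and 10.4.3.

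The cost is definition wording and one derived variable, with no added biopsy and no treatment rule. The downsides are slightly more derivation work and possibly a somewhat higher event count than if every case needed a marrow taken after day 42.
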